## 2. RESEARCH DESIGN AND METHODS

### 2.1 CLASSIFICATION AND METHODOLOGICAL DESIGNS

The proposed pilot study is designed as a prospective, cross-over trial. Over a 13.5-month period, we will recruit 30 outpatients with chronic non-severe hyponatremia (PNa 125 to 132 mmol/L) confirmed to be due to SIADH. Subjects will not be withdrawn from any known effective therapy for chronic hyponatremia for the purpose of participating in this study. Following enrollment, patients will be randomly assigned on 1:1 ratio to one of two sequence groups. Patients assigned to group "Urea ON, then Urea OFF" will receive oral urea for 42 ± 3 days (period 1), followed by a 10 ± 4-day period in which all patients will be off urea (washout period). Patients then will be off urea for 42 ± 3 days (period 2). Patients assigned to group "Urea OFF, then Urea ON" will be off urea therapy for 42 ± 3 days (period 1), and following a 10 ± 4-day washout period then they will initiate urea for 42 ± 3 days (period 2). Patients will have PNa assessed at baseline and on days 7 ± 2, 14 ± 2, and 42 ± 3 during periods 1 and 2 of the study and will undergo neurocognitive and postural control and stability testing on days 0 and 42 of each of the study periods. All patients will be advised to restrict their fluid intake to ≤1.2 liters during periods 1 and 2.

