### 2.4 STUDY ENDPOINTS

### 2.5 STATISTICAL ANALYSIS

#### 2.5.1 Sample Size Determination

This pilot study aims to assess the feasibility of conducting a future clinical trial. Thus, the sample size of 30 patients was determined based on clinical and logistical reasons rather than statistical requirements. For Aim 1, we anticipate identifying approximately 300 potentially eligible patients during the 13.5 months of recruitment (~22 per month). A 95% confidence interval (CI) for the randomization rate provides a 3% margin of error (MoE) assuming the true rate was 10% (~3 per month). If the underlying dropout and adherence rates were 80%, a sample size of 30 provides 14% MoE for 95% CIs. For Aim 2, our sample size provides 83% power to detect a standardized mean difference of 0.65 for our efficacy outcomes. We are not powered to detect smaller effect sizes. However, since this is a proof-of-concept study, detecting a moderate-to-large effect size increases our confidence in the potential efficacy of urea. For Aim 3, underlying adverse events rates of 5% to 10%, 95% CIs will provide 8% to 11% MoE, respectively.

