#### 2.5.3 Efficacy Analysis

This study is not powered to establish the efficacy of urea on increasing PNa or improving neurocognition and/or postural control/stability. However, to justify a future large, randomized clinical trial of urea, we need proof of concept data that urea has potential benefits for these outcomes. We will summarize patient demographics and clinical characteristics by study group. For the primary outcomes (PNa, neurocognition scores, postural control/stability scores) and secondary exploratory outcome (SF-12 scores), we will calculate change from baseline to day 42 in each treatment period. We will analyze these data using a linear mixed effects model with patient-specific random effects to account for within-patient correlations. Model predictors will include treatment,

period and treatment period interaction. Coefficients and 95% CIs will be used to quantify the treatment effect. We will also use this model to assess period effect and carryover effects (treatment period interaction).

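### The random-effect model for two own-baseline changes per patient may give too narrow a CI for the period-averaged urea effect if those changes are negatively correlated

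*Combined protocol and SAP*

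**What the plan says.** Section 2.1 has patients "randomly assigned on 1:1 ratio to one of two sequence groups", with neurocognitive and "stability testing on days 0 and 42 of each of the study periods". Plasma sodium is also measured at the start and at day 42 of both periods. Section 2.5.3 then states, for plasma sodium, the neurocognitive and postural scores and the SF-12, that "we will calculate change from baseline to day 42 in each treatment period". Each patient therefore supplies two change scores, each taken from that period's own baseline.

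These are analysed with a "linear mixed effects model with patient-specific random effects to account for within-patient correlations". The predictors are treatment, "period and treatment period interaction". "Coefficients and 95% CIs will be used to quantify the treatment effect", and the same model is used to judge period and carryover effects. Section 2.5.3 does not state a covariance structure, whether the variance may go below zero, a degrees-of-freedom method, or how treatment and period are coded.

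**The concern.** A patient random intercept describes a stable level that raises or lowers all of a patient's values together. Taking each period's change from its own day 0 has already subtracted that level. What is left may be uncorrelated between periods. It may also be negatively correlated, because the closest pair of visits (day 42 of period 1 and day 0 of period 2, about 10 days apart) enters the two changes with opposite signs.

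A negative correlation makes the ON minus OFF difference within a patient more variable than two independent values would be. A random-intercept variance bounded at zero cannot express this. It is estimated as zero, the between-patient and within-patient mean squares are pooled, and the standard error of the within-patient urea effect comes out too small. The carryover test errs the other way, because pooling inflates its standard error. These intervals are what section 2.5.3 offers as proof of concept for a larger trial.

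**Working it through.** **The plan's own figure.** The only stated figure that depends on the within-patient correlation ρ of the changes is in section 2.5.1: "For Aim 2, our sample size provides 83% power to detect a standardized mean difference of 0.65 for our efficacy outcomes". Alpha, sidedness, the standardising SD and ρ are not given. Take two-sided 5%, n = 30, and 0.65 in SDs of the change score. The noncentrality is 0.65√30 / √(2(1-ρ)) = 3.56 / √(2(1-ρ)).
- ρ = 0: 3.56/1.414 = 2.52, power 71% (68% with t, 28 df).
- ρ = 0.25: 3.56/1.225 = 2.91, power 83% (normal). With t, 83% needs ρ of about 0.30.
- If 0.65 is instead in SDs of the within-patient difference, power is about 93-95%.

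So the 83% cannot be reproduced without an added assumption. It is not shown to be wrong, and it does not document ρ.

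**Possible size of ρ.** The visits fall on days 0, 42, 52 and 94 (42-day periods and a 10-day washout, section 2.1). Let r(d) be the correlation of two measurements d days apart. Then

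ρ = [2r(52) - r(10) - r(94)] / [2(1 - r(42))].

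- Equally correlated visits: the numerator is 0, so ρ = 0.
- Exponential decay with r(42) = 0.5 (assumed): (2×0.424 - 0.848 - 0.212)/1.0 = -0.21.
- r(42) from 0.9 down to 0.1 (assumed): ρ from -0.05 to about -0.26. A decay constant of 20 days gives -0.27.
- Independent visit-to-visit noise shrinks this. With r(42) = 0.5 and noise variance equal to the serial variance, ρ = -0.212/3 = -0.07.
- A patient-level response shared by both periods, with variance k times the single-measurement error variance (assumed), gives ρ = k/(k+2): +0.11, +0.20 and +0.33 for k = 0.25, 0.5 and 1.

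**Effect on inference.** Assume 15 patients per sequence and complete data. The within-patient mean square W has expectation σ²(1-ρ) and the between-patient mean square B has expectation σ²(1+ρ), each on 28 df. The true variance of the period-averaged effect is σ²(1-ρ)/15. REML with a bounded random intercept uses W when B ≥ W and the pooled (W+B)/2 when B < W. Results are from 2,000,000 simulated null trials per row.

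| ρ | Variance set to 0 | Mean SE / true SE | Type I error, urea (t, 28 df) | Same, within-patient-difference analysis | Size of carryover test |
|---|---|---|---|---|---|
| 0.30 | 5% | 0.99 | 5.0% | 5.0% | 4.9% |
| 0.20 | 15% | 0.98 | 5.1% | 5.0% | 4.8% |
| 0 | 50% | 0.96 | 5.6% | 5.0% | 3.9% |
| -0.14 | 77% | 0.92 | 6.5% | 5.0% | 3.0% |
| -0.27 | 93% | 0.88 | 7.6% | 5.0% | 2.0% |

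Under reference-cell coding of the planned interaction model, the treatment coefficient is the period 1 between-patient contrast. Its standard error uses W + B, which pooling leaves unchanged. Its coverage is about 95.4% at every ρ tested. With 24 patients instead of 30, the results for the period-averaged effect are similar.

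**The case against.** The strongest reply is that the sign of ρ is unknown and the design contains a reason for it to be positive. Fluid restriction starts at day 0 of each period and is lifted for the washout (section 2.2), so a patient's own response to restriction enters both changes with the same sign. Suppose the serial component is 30-50% of the variance with a decay constant of 20-60 days. A shared-response SD of about 0.25-0.48 outcome SDs would then cancel the negative covariance completely. If the 83% power rests on ρ of about 0.25-0.30, the planners may have expected a positive correlation. This stands: the documents do not support a reader's inference that the intervals will be too narrow.

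Two further inferences also fail. One is that a random effect cannot handle zero correlation. It can, with variance zero, and the only loss is occasional truncation (5.6% against 5.0%). The other is that the standard errors of all ten primary efficacy outcomes (items 6-15 of the synopsis endpoint list) and the SF-12 are understated. That depends on which contrast is reported, and the period 1 coefficient is unaffected.

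It is also fair that the text is under-specified rather than plainly wrong. An unbounded variance or a compound-symmetric residual would remove the problem, and nothing in section 2.5.3 forbids either. Finally, this is a pilot in which "the sample size of 30 patients was determined based on clinical and logistical reasons", and no go/no-go rule depends on these intervals. That limits the consequence, but it does not argue against a method that is valid for either sign.

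**Conclusion.** The concern holds in a conditional form. As written, section 2.5.3 leaves open a bounded random intercept. If the two own-baseline changes have a correlation of 0 to -0.27, that model makes the standard error of the period-averaged urea effect about 4-12% too small on average, with type I error of about 5.6-7.6% in place of 5%. It also makes the carryover test conservative, with size about 3.9% to 2.0%. At correlations of about 0.2-0.3 or more the loss is negligible.

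These figures assume 15 patients per sequence, complete data, equal variances, a variance bounded at zero and t limits on 28 df. The correlations are assumed, since the documents give none. The effect is modest. It is worth correcting because the remedy is cheap and valid whatever the sign of the correlation.

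**What to change.** In section 2.5.3, replace the patient-specific random effects by an unstructured 2x2 within-patient covariance across the two periods, with negative covariance allowed, and Kenward-Roger degrees of freedom.

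In the same place, define the urea effect as the period-averaged ON minus OFF contrast, through centred coding or an explicit contrast. This second part is needed. If only the covariance is changed, reference-cell coding still leaves the treatment coefficient as a period 1 comparison between patients.

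With both parts in place and complete data, the analysis equals comparing within-patient period differences between the two sequences on 28 df, which held 5.0% at every correlation checked. The cost is a line or two of text and a changed model specification. The intervals may be slightly wider.

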# 2.5.4 Safety Analysis

This pilot study is not designed to comprehensively identify low frequency adverse events. Nonetheless, we will report all adverse events/side effects during urea therapy. We will report to the sponsor the seriousness and severity of each event and whether the event was potentially related to urea. We recognize that osmotic demyelination syndrome is a complication of overly rapid correction of PNa (increase in PNa >8 mmol/L/24h) in patients with severe hyponatremia (PNa ≤120 mmol/L). However, we do not believe this is a concern in our study as patients with PNa ≥125 mmol/L who do not have serious liver disease (an exclusion criterion for our study) have a negligible risk of osmotic demyelination syndrome if overly rapid correction of hyponatremia occurs.

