- n. To assess the change in amplitude scaling of posture control and stability using dynamic representation of upright stance in patients with chronic hyponatremia due to SIADH from baseline to day 42 of urea therapy
- o. To determine the number and proportion of patients with chronic hyponatremia due to SIADH enrolled in the study with adverse events related to the use of urea
- p. To determine the presence and nature of adverse events in patients with chronic hyponatremia due to SIADH related to urea therapy.

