## **1.2 SPECIFIC AIMS**

Hypotheses:

- a. We hypothesize that we will be able to recruit at least 10% of eligible patients with chronic hyponatremia due to SIADH.
- b. We hypothesize that we will be able to document at least 80% compliance with prescribed urea doses in patients with chronic hyponatremia due to SIADH.
- c. We hypothesize that urea will significantly increase the plasma sodium concentration at day 42 compared with the baseline level in patients with chronic hyponatremia due to SIADH.
- d. We hypothesize that urea will significantly improve the scores on neurocognitive and posture control and stability assessments at day 42 compared with the baseline scores in patients with chronic hyponatremia due to SIADH.
- e. We hypothesize that adverse events related to the use of urea in patients with chronic hyponatremia due to SIADH will be very uncommon.

Specific Aims:

Primary:

- 1. To assess the feasibility of recruiting patients with chronic hyponatremia due to SIADH into a study of oral urea and to evaluate their adherence to oral urea.
- 2. To assess the effect of oral urea on plasma sodium concentration and on neurocognitive function and postural control and stability in patients with chronic hyponatremia due to SIADH.
- 3. To explore the safety of oral urea in patients with chronic hyponatremia due to SIADH.

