#### Follow-up research assessments:

All patients in group "Urea ON, then Urea OFF" will have scheduled follow up assessments on days 7, 14, and 42 as follows:

- Day 7: Phone interview and basic metabolic panel (BMP).
- Day 14: Phone interview and BMP. More boxes of Ure-Na will be mailed if needed to complete the study.
- Day 42: same assessment as in the baseline study visit

The phone interviews visits will focus on assessing side effects, tolerability, and adherence to urea and as appropriate, dose titration of urea. Side effects and tolerability will be assessed with questionnaires (See Medication Side Effects Questionnaire and Medication Acceptability Questionnaire). Patient also will be asked to bring their study diary to the in-person clinic visits to track their adherence to fluid restriction and urea. Visits at day 0 and day 42 will take place in the Neuromuscular Research Laboratory at the University of Pittsburgh. BMP assessment on days 7, 14 will take place at the UPMC clinical laboratory of patient's choice. At the 42-day visit, patients will be asked to return their study diary and any urea doses they did not consume. During period 1 of the study, patients randomized to group "Urea OFF, then Urea ON" will undergo same assessments as outlined for group "Urea ON, then Urea OFF", although they will not be asked about tolerability or adherence to urea as they will not be on this treatment during this period.

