- A co-investigator will test patients' balance while standing on a specialized piece of equipment. Patient will be asked to stand on both legs on top of a platform in a dynamic moving environment. Patient will go through six conditions, with three trials per condition, lasting about 20 seconds each. Patient will be asked to look forward, and stand as motionless as possible with your arms at your sides. The six conditions include the possibility of moving surroundings or moving base of support. If patient move or lose his/her balance during the procedures, patient will be asked to repeat that part again. Patient will be supported by means of a harness in the equipment to make sure he/she cannot fall over while performing the tests.
- The research coordinator will instruct the patient to restrict his/her fluid intake to no more 1200 mL/day for the next 42 ± 3 days. The research coordinator will provide the patient with a diary to record daily fluid intake.
- Patients will be randomized prior to or at the first study visit (Period 1 Day 0) following completion of baseline assessments. Our biostatistician will generate the randomization list using permuted blocks of random block sizes of 4 and 6 and our systems analyst will load the list into RedCAP. To preserve allocation concealment for consecutively enrolled participants, we will use the randomization module in RedCAP to assign each participant 1:1 to either On-to-Off Urea sequence or Off-to-On Urea sequence.
- If patient is randomized to take On-to-Off Urea sequence then the research coordinator will give the patient 48 urea powder pouches with instructions on how to take the urea every day. The research coordinator will provide the patient with a diary to record patient's daily urea intake.
- This visit will last approximately 2.5 hours.

Second study visit (Day 7 of Period 1)

- The research coordinator will call the patient on the phone to ask some questions about any new symptoms patient might have experienced since his/her last visit.
- The research coordinator will direct the patient to go the UPMC clinical laboratory of the patient's choice that day to have his blood drawn for analysis of a basic metabolic panel.
- If patient is taking urea, we might call the participant on the phone again to ask to change the dose of urea depending on the sodium level results.
- This visit will last approximately 20 minutes.

Third study visit (Day 14 of Period 1)

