- The research coordinator will draw approximately 14 mL of patient's blood and send the specimen promptly to the UPMC Presbyterian clinical laboratory for processing and analysis of the following: basic metabolic panel, plasma osmolality, and plasma uric acid.
- Patient will complete the SF-12 survey with pen and paper.
- A co-investigator will test patients' reactions and decision making using specialized software on a tablet computer.
- A co-investigator will test patients' balance while standing on a specialized piece of equipment. Patient will be asked to stand on both legs on top of a platform in a dynamic moving environment. Patient will go through six conditions, with three trials per condition, lasting about 20 seconds each. Patient will be asked to look forward, and stand as motionless as possible with your arms at your sides. The six conditions

include the possibility of moving surroundings or moving base of support. If patient move or lose his/her balance during the procedures, patient will be asked to repeat that part again. Patient will be supported by means of a harness in the equipment to make sure he/she cannot fall over while performing the tests.

- The research coordinator will ask patient to stop fluid restriction.
- If patient is taking urea then the research coordinator will instruct the patient to stop taking urea and return all the urea pouches he/she did not use to the research coordinator.
- The research coordinator will provide the patient with a container with instructions to collect urine for 24 hours prior to next study visit.
- This visit will last approximately 2.5 hours.

Reminder telephone call

• The research coordinator will call the patient on the phone 48-72 hours before the next study visit to remind him/her of the upcoming study visit.

Fifth study visit (Day 0 of Period 2)

- Patient will come in person to the University of Pittsburgh Neuromuscular Research Laboratory located at [name].
- Patient will bring the container with the 24-hour urine collection he/she started the day prior. The research coordinator will send the specimen promptly to the UPMC Presbyterian clinical laboratory for processing and analysis of the following: creatinine, urea nitrogen, uric acid, osmolality, sodium, and potassium.

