### 2.3.5. Breaking the Blind

The proposed clinical study will not be blinded.

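### The safety analysis plans no off-urea summary or ON/OFF comparison of adverse events, although new-symptom questions are asked in both crossover periods

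*Combined protocol and SAP*

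**What the plan says.** Section 2.5.4 makes one reporting commitment for adverse events: "we will report all adverse events/side effects during urea therapy". Seriousness, severity and possible relation to urea are then reported to the sponsor for each event. The primary objectives count patients "enrolled in the study with adverse events related to the use of urea" and describe those events, and endpoints 16 and 17 in the synopsis match them. Hypothesis e in Section 1.2 is that "adverse events related to the use of urea in patients with chronic hyponatremia due to SIADH will be very uncommon". Section 2.5.1 gives the Aim 3 precision as 8% to 11% for event rates of 5% to 10%.

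Section 2.2 (Research activities) has the coordinator telephone patients on days 7 and 14 of each period to "ask some questions about any new symptoms patient might have experienced since his/her last visit". A similar question is listed at each day 42 visit. None of these questions depends on whether the patient is taking urea. Under Follow-up research assessments, patients off urea have the same assessments, "although they will not be asked about tolerability or adherence to urea as they will not be on this treatment during this period". The Day 0 visit of Period 2, which ends the washout, lists no symptom question.

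Section 2.3.5 states: "The proposed clinical study will not be blinded".

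**The concern.** In this crossover every patient also supplies an off-urea period as long as the urea period, under the same fluid restriction. The efficacy analysis in Section 2.5.3 uses both periods. The safety analysis specifies nothing for the off-urea one.

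The symptoms that Section 2.3 expects from urea also occur without it. Without an off-urea rate, a reader of the final report cannot tell whether the number of patients with nausea or headache on urea exceeds what the same patients report off it. What remains is a judgement of relatedness by staff who know the treatment. Safety is one of the three primary aims, and the pilot is meant to inform a larger trial, so the missing background rate would be felt at the next design stage.

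**Working it through.** **1. The plan's own precision.** Inputs: N = 30 and rates of 5% and 10% (Section 2.5.1). Half-width = 1.96 × √(p(1−p)/30).
- p = 0.05: 1.96 × √(0.0475/30) = 0.078 (stated 8%).
- p = 0.10: 1.96 × √(0.09/30) = 0.107 (stated 11%).

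Both reproduce. They are one-sample figures, consistent with a plan that has no off-urea comparison.

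**2. Size of the background.** The documents give no off-urea symptom rate, so p below is an assumption: the share of patients with at least one such symptom in any 42 days regardless of urea. Expected number = 30p; chance of at least one = 1 − (1−p)^30.

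| Assumed p | Expected patients of 30 | Chance of at least one |
|---|---|---|
| 5% | 1.5 | 0.785 |
| 10% | 3 | 0.958 |
| 20% | 6 | 0.999 |

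The first two rows equal the event rates that the plan expects. They count any symptom; endpoint 16 counts related ones, so this is the pool from which relatedness would be judged.

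**3. What the on-urea figure cannot show.** Suppose 30% of patients report a symptom on urea (assumed). The on-urea summary is 30% ± 1.96 × √(0.21/30) = ± 16 points whatever the off-urea rate. For the within-patient difference, half-width = 1.96 × √((b + c − (b−c)²)/30), where b and c are the proportions with a symptom only ON and only OFF. The range is for a within-patient correlation of 0.3 (smaller margin) to 0 (larger).

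| Assumed ON | Assumed OFF | Difference (points) | Margin (points) |
|---|---|---|---|
| 30% | 5% | 25 | 16 to 18 |
| 30% | 10% | 20 | 17 to 20 |
| 30% | 20% | 10 | 18 to 22 |
| 30% | 30% | 0 | 19 to 23 |
| 10% | 5% | 5 | 11 to 13 |

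The first four rows give the same on-urea report, while the excess over background runs from 0 to 25 points.

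**4. One case worked through.** ON 20%, OFF 10%, independent: both = 0.02, b = 0.18, c = 0.08. Margin = 1.96 × √((0.26 − 0.01)/30) = 0.179, about 18 points around a difference of 10. All these margins assume 30 complete pairs.

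**5. Is the comparison already in the data?** Largely, with three gaps.
- The Day 7 call of Period 2 asks only about the time since the preceding visit, which is Day 0 of Period 2. No listed symptom question therefore covers the washout of 10 ± 4 days.
- Section 8.1 names only clinically important events for the adverse event form, so minor off-urea symptoms may not be on it.
- Section 10 ends data collection when a patient is withdrawn for persistent symptoms. Such a patient in the urea-first sequence would have no off-urea record.

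**The case against.** A reader might infer that off-urea events will be excluded or thrown away. The documents do not say so. Section 2.5.4 states what will be reported and excludes nothing. The case report forms cover adverse experiences without a treatment limit (Section 2.5.6), staff report all adverse events to an investigator (Section 9.2), and collected events are reviewed for benefit and risk (Section 9.3). That objection stands. These are routes for capture and oversight, however, and none specifies an off-urea summary.

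A reader might also infer that washout symptoms can never surface. That goes too far: Section 2.3.8 requires a review of health changes, admissions and new medicines at every study visit, which could bring out a symptom. Section 2.3.3 also gives urea a half-life of 2.5 h with elimination within 12 h, so late effects are unlikely. What stands is that no explicit symptom question is listed at that visit.

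Nor would an ON/OFF difference be free of bias. Patients know when they take urea, the margins are wide, and withdrawal may remove the off-urea record of the least tolerant patients. The table would be descriptive. It would not change endpoints 16 and 17, which count related events and which an on-urea report matches. Aim 3 is also only exploratory.

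Finally, the Medication Side Effects Questionnaire and the manual of procedures are not in the text reviewed. Whether the questionnaire refers to urea, or is used off urea, cannot be judged here.

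**Conclusion.** The point holds as a gap in the specified analysis. The plan commits to on-urea reporting, names no off-urea summary or ON/OFF comparison, and asks the needed questions in both periods. At assumed background rates of 5% to 20%, 1.5 to 6 of 30 patients would have a symptom on urea without urea causing it, as many as the plan expects in total or more. That size rests entirely on the assumed rates.

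It would be too strong to say that endpoints 16 and 17 or hypothesis e cannot be addressed, or that the added table would settle causation: relatedness stays an open-label judgement, and a 10-point difference would carry a margin of about 18 points. The table gives those endpoints a context that they now lack. Sample size, power and efficacy analyses are unaffected. The change is worth making while symptoms are still being collected, since an analyst cannot later recover questions that were not asked or answers that were not recorded.

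**What to change.** - **Section 2.5.4:** report all adverse events and each listed symptom by interval (ON, OFF, washout). Give the number and proportion of patients affected in ON and in OFF, and the within-patient difference with its 95% CI, labelled as descriptive, imprecise and open label.
- **Incomplete pairs:** state how many patients lack an ON or OFF record because of withdrawal under Section 10, and keep them in the per-interval counts.
- **Section 2.2:** ask the same symptom items, worded without reference to urea, on days 7, 14 and 42 of both periods, and add them at Day 0 of Period 2.
- **Recording:** record the answers whether or not they meet the Section 8.1 threshold for the adverse event form.
- **Endpoints 16 and 17:** leave as written, and present the ON/OFF table beside them.

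The cost is wording in two sections, one extra table and slightly longer contacts at visits and calls that already take place. No extra patients are needed.
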